6.3 Pregnancy and Reproduction

6.3.1 Women:

- Women are considered post-menopausal and not of child bearing potential if they have had 12 months of natural (spontaneous) amenorrhea with an appropriate clinical profile (i.e. age appropriate, history of vasomotor symptoms) or six months of spontaneous amenorrhea with serum FSH levels >40 mIU/mL and estradiol < 20 pg/mL or have had surgical bilateral oophorectomy with or without hysterectomy at least six weeks prior to enrollment in the study. In the case of oophorectomy alone, only when the reproductive status of the woman has been confirmed by follow up of hormone level assessment is she considered not of child bearing potential.
- Women of child-bearing potential, defined as all women physiologically capable of becoming pregnant, must use highly effective contraception during study treatment and for 16 weeks after study discontinuation. Highly effective contraception is defined as either
 - True abstinence: When this is the line with the preferred and usual lifestyle of the subject. Periodic abstinence (e.g. calendar, ovulation, symptothermal, post-ovulation methods) and withdrawal are not acceptable methods of contraception
 - Sterilization: Surgical bilateral oophorectomy, with or without hysterectomy, or tubal ligation at least six weeks prior to study enrollment. In the case of oophorectomy alone, only when the reproductive status of the woman has been confirmed by follow up hormone level assessment.
 - Male partner sterilization (with appropriate post-vasectomy documentation of the absence of sperm in the ejaculate). For female patients participating in the study, the vasectomized male partner should be the sole partner for that patient.
 - Use of a combination of any two of the following:
 - Placement of an intrauterine device (IUD) or intrauterine system (IUS)
 - Barrier methods of contraception: Condom or occlusive cap (diaphragm or cervical vault caps) with spermicidal form/gel/film/cream/vaginal suppository

NOTE: Oral contraception as well as injected, implanted, or local hormonal methods of contraception are not acceptable methods of contraception for women of child bearing potential as buparlisib potentially decreases the effectiveness of hormonal contraceptives

- Women of child-bearing potential must have a negative serum pregnancy test at screening

MEMORIAL SLOAN-KETTERING CANCER CENTER IRB PROTOCOL

IRB#: 14-177 A(5)

- In addition to having a negative pregnancy test confirmed at screening, all female participants of child bearing potential must have a negative serum pregnancy test confirmed within 48 hours prior to dosing with the study drug.

6.3.2 Men:

- Fertile males, defined as all male subjects physiologically capable of conceiving offspring, must use a condom during study treatment and for 16 weeks after study discontinuation and should not father a child in this period
- Female partner of a male study subject should use a highly effective method of contraception while the male partner is receiving the study agent and for 16 weeks after the final dose of the study therapy

6.2.1.3 Inclusion of women, minorities or other underrepresented populations

Buparlisib is not known to differentially affect subpopulations, including women, minorities, or other underrepresented groups. The eligibility and exclusion criteria are not expected to differentially impact recruitment or retention of these subpopulations.

7.0 RECRUITMENT PLAN

MSKCC has long been a center of clinical excellence in PCNSL and is a nationally renowned referral center for patient with PCNSL. Additionally, we will work closely with the MSKCC Lymphoma service to enroll patients with SCNSL. Patients will be recruited from the neurology and lymphoma clinics at Memorial Sloan-Kettering Cancer Center. All patients will be seen by an attending physician who is an investigator on the trial. All patients enrolled on the trial must sign written informed consent. There is no gender or racial restriction. If accrual is inadequately slow, then we will reach out and collaborate with other centers.

8.0 PRETREATMENT EVALUATION

8.1 General Requirements

All participant need to fulfill inclusion and exclusion criteria and have signed an informed consent form.

A complete history, vital signs (including blood pressure, pulse, respiratory rate, temperature, weight and height), physical, and neurological examination (to include documentation of the patients Karnofsky performance status; Appendix 6) and NANO score as well as neuro-imaging (including contrast-enhanced MRI/CT brain and total spine) and/or CSF evaluation (including cell count, total protein and glucose as well as cytology) confirming tumor progression will be performed on all patients. All patients will need a PET body and brain for staging purposes prior to study enrollment. The scans done prior to study entry documenting progression will be reviewed by the principal investigator. The baseline scan or CSF evaluation should be performed 21 days of registration. Prestudy laboratory tests need to included CBC with differential, platelets, coagulation panel (including PT, PTT, INR), sodium, potassium, calcium, AST, ALT, alkaline phosphatase, total bilirubin, fasting plasma glucose, creatinine, lipid panel, HbA1c, 8 hour fasting C-peptide, amylase, lipase, LDH, a screening hepatitis B and C serology, a screening HIV serology, serum pregnancy test for women of childbearing potential. Prestudy laboratory tests must be obtained within 21days of registration.

MEMORIAL SLOAN-KETTERING CANCER CENTER IRB PROTOCOL

IRB#: 14-177 A(5)

Documentation of tumor diagnosis. Following registration, slides from the most recent pre-registration biopsy and/or CSF cytology must be submitted for review and confirmation of diagnosis. Additionally, 20 unstained slides from the initial tissue diagnosis must be submitted for exploratory studies.

A contrast enhanced CT scan of the chest, abdomen and pelvis, ophthalmologic evaluation including slit lamp exam, 12-lead ECG, ECHO/MUGA, as well as a bone marrow aspirate must be performed for staging purposes. These staging tests must be obtained within 21 days of registration.

Patient need to complete the PHQ-9 and GAD7 self rating mood scale within 21 days of registration (see Appendix 6).

Please also see Table 6 for an overview of testing required prior to enrollment into the trial.

9.0 TREATMENT/INTERVENTION PLAN

All participant will initiate treatment at 100 mg Buparlisib PO within 96 hours of registration. The study drug will be administered with a flat-fixed dose, and not by body weight or body surface area. For the purpose of this trial a cycle will be defined as 28 days. There will be no breaks between dosing cycles. The study drug buparlisib will be self-administered. The investigator will instruct the participant to take the study drug exactly as specified in the protocol. Buparlisib will be administered on a continuous once daily schedule. Patients will be asked to keep a pill diary. Treatment will continue until one of the events in Section 13 occurs.

9.1 Dose Modifications/Delays

For participants who are unable to tolerate the protocol-specified dosing schedule, dose adjustments are permitted in order to keep the participant on study drug. If administration of buparlisib must be interrupted because of unacceptable toxicity, drug dosing will be interrupted or modified according to the rules described in Table 11. Any planned variance from these guidelines in the view of patient safety must be previously discussed with the sponsor unless there is an urgent need for action. Any changes in buparlisib administration must be recorded in the pill diary.

All dose modifications, interruptions, or discontinuations must be based on the worse preceding toxicity as graded using the CTEP Version 4.0 of the NCI Common Terminology Criteria for Adverse Events (CTCAE), which can be found on the website at http://ctep.cancer.gov/protocolDevelopment/electronic_applications/ctc.htm. In the case of toxicity, appropriate medical treatment should be used, including anti-emetics, anti-diarrheals, etc.

All adverse events experienced by participants will be collected from the time of the first dose of study treatment through the study until the final study visit. Participants continuing to experience toxicity at the end of treatment visits may be contacted for additional assessments until the toxicity has resolved or is deemed irreversible.

All participants will be initially treated at Dose Level 0. A buparlisib dose reduction will be administered at 20 mg below the current dose. The dose reduction steps are outlined in Table 5.

Table 5: Dose reduction steps for Buparlisib

Buparlisib dose levels and dose reductions*

Starting dose level – 0	100 mg/day continuously
Dose level – 1	80 mg/day continuously
Dose level – 2	100 mg/day 5 days out of 7
Dose level – 3	60 mg/day continuously
Dose level – 4	80 mg/day 5 days out of 7

*Dose reduction should be based on the worst preceding toxicity

Table 11 should be adhered to for all toxicities as noted below, regardless of suspected attribution unless otherwise specifically noted within the table. For situations where a participant experiences a toxicity which the treating investigator feels is unrelated to treatment with buparlisib, but which requires a hold or reduction of the study drug according to Table 11, maintaining treatment with the study drug is allowable following discussion with the Principal Investigator.

When treatment must be held pending resolution of toxicity to grade 1 or return to baseline, and the toxicity is a lab abnormality, in cases where the participant had a pre-existing laboratory abnormality at baseline, the toxicity can be considered “resolved from a hold perspective when it has resolved to within 1 grade of the baseline value.

NOTE: For the purposes of data entry, value from screening assessments should be entered in as “baseline values.” However, true “baseline values” for the purpose of dose modifications on study will be considered the last assessments or tests performed prior to initiation of study therapy.

Exception: In instances where the value within 1 grade of the baseline value would still require a hold, continue to hold until resolution of toxicity to grade 1 or return to baseline.

Participants who experience an adverse event that requires a treatment delay or dose reduction should be monitored with appropriate laboratory testing or other clinical evaluation at least weekly until resolution.

Following a dose delay which resumes mid cycle, day 1 procedures not associated with the adverse event do not need to be repeated.

No more than 4 levels of dose reduction are permitted in this study. Participants cannot be treated below dose level -4. If a participant whose buparlisib dose has been reduced by 4 dose levels requires another dose reduction, treatment on study must be stopped unless the participant has benefited from the study, in which case the investigator will contact the Principal Investigator to determine if the participant will remain in the study.

A treatment delay of up to 28 days is permitted. If the toxicity has not resolved after a 4 week delay, the participant must be removed from study treatment unless the participant has benefited from the study, in which case, the investigator may contact the Principal Investigator to determine if the participant will remain in the study.

Dose re-escalation is never permitted in this study.

MEMORIAL SLOAN-KETTERING CANCER CENTER IRB PROTOCOL

IRB#: 14-177 A(5)

Cycle length will be 4 weeks (28 days), even if treatment is held for toxicity. There is no stopping in counting cycles/days for those periods where a subject's drug is withheld. All study evaluations and treatments should continue as if study treatment is not being held.

Participants whose treatment is interrupted or permanently discontinued due to an adverse event or clinically significant laboratory value must be followed as outlined in Table 11 at least once a week for 4 weeks and subsequently at 4-week intervals until resolution or stabilization of the event, whichever comes first. All participants must be followed for adverse events and serious adverse events for 30 days following the last dose of buparlisib.

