AST or ALT	
Grade 1 (> ULN – $3.0 \times ULN$)	Maintain dose level with LFTs* monitored per protocol

MEMORIAL SLOAN-KETTERING CANCER CENTER
IRB PROTOCOL

IRB#: 14-177 A(5)

Grade 2 (> 3.0 - 5.0 x ULN) without total bilirubin elevation to > 2.0 x ULN	Can continue treatment at ↓ 1 dose level
Grade 3 (> 5.0 - 20.0 x ULN) without total bilirubin elevation to > 2.0 x ULN	Omit dose until resolved to ≤ Grade 1, then ↓ 1 dose level** If no recovery in ≤28 days, discontinue buparlisib permanently
Grade 4 (> 20.0 x ULN) without bilirubin elevation to > 2.0 x ULN	Discontinue buparlisib permanently
AST or ALT and concurrent Bilirubin	
AST or ALT > 3.0 x ULN and total bilirubin > 2.0 x ULN	Permanently discontinue buparlisib***

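### Section 9.1 sets every dose reduction at 20 mg below the current dose, but Table 5 follows that rule only at the first of its four steps

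*Combined protocol and SAP*

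**What the plan says.** Section 9.1 (Dose Modifications/Delays) starts every participant at level 0 and then gives a rule in milligrams: "A buparlisib dose reduction will be administered at 20 mg below the current dose". The next sentence reads "The dose reduction steps are outlined in Table 5". Table 5, titled "Dose reduction steps for Buparlisib", lists:

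- level 0: 100 mg daily
- level -1: 80 mg daily
- level -2: "100 mg/day 5 days out of 7"
- level -3: 60 mg daily
- level -4: 80 mg on 5 of 7 days

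The same section caps the ladder ("No more than 4 levels of dose reduction are permitted in this study"), sets level -4 as the floor, and adds: "Dose re-escalation is never permitted in this study".

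The rest of the protocol works in levels. A footnote to Table 3 (Section 4.2) sends reductions to Table 5. Section 9.1 says that "drug dosing will be interrupted or modified according to the rules described in Table 11", and Table 11 (Section 11.2) states its reductions in levels; for grade 2 AST or ALT, for example, it says "Can continue treatment at ↓ 1 dose level". Table 12 (Section 11.3) orders a one-level reduction for grade 2 pneumonitis and cites Table 5.

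**The concern.** Two adjacent statements give different answers to the same prescribing question. The milligram rule refers to the current dose, so it applies again at each reduction. Table 5 does not descend in 20 mg steps after the first one, because it changes the schedule as well as the strength.

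The misreading is plausible. Section 9.0 describes continuous once-daily dosing, and re-escalation is prohibited. A prescriber with a patient on 80 mg daily who sees 100 mg at the next level may doubt that this is a reduction and turn to the sentence, which points to 60 mg daily. That patient misses level -2 and cannot return to it. Section 9.1 says dose adjustment is meant to keep participants on drug, and skipping a permitted level works against that aim. Section 7.0 also allows other centers to join if accrual is slow, so the rule may be read by staff outside the lead site.

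**Working it through.** **Inputs.** Strength and schedule at each level come from Table 5; the 20 mg rule comes from the text of Section 9.1.

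**Formulas.** Weekly dose = mg per dosing day × dosing days per week. Mean daily dose = weekly dose / 7. Each step is the level minus the level above it.

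| Level | mg × days | mg/week | Mean mg/day | Step, mg per dosing day | Step, mean mg/day |
|---|---|---|---|---|---|
| 0 | 100 × 7 | 700 | 100.0 | – | – |
| -1 | 80 × 7 | 560 | 80.0 | -20 | -20.0 |
| -2 | 100 × 5 | 500 | 71.4 | +20 | -8.6 |
| -3 | 60 × 7 | 420 | 60.0 | -40 | -11.4 |
| -4 | 80 × 5 | 400 | 57.1 | +20 | -2.9 |

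**Does the stated 20 mg reproduce?** Only for level 0 to -1. The other three steps fail on both measures. Weekly dose falls at every step, so Table 5 is a valid descending ladder.

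**Sentence against table, step by step.**

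- From level 0: 100 - 20 = 80 mg daily, 560 mg/week. This is level -1, so the two agree.
- From level -1: 80 - 20 = 60 mg daily, 420 mg/week. This is level -3. Table 5 gives level -2, 500 mg/week. Difference 500 - 420 = 80 mg/week; 80/500 = 16% less.
- From level -2, keeping the 5-of-7 schedule: 100 - 20 = 80 mg, × 5 = 400 mg/week. This is level -4. Table 5 gives level -3, 420 mg/week. Difference 420 - 400 = 20 mg/week; 20/420 = 4.8% less.

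**The sentence applied throughout.** Four reductions would run 100, 80, 60, 40, 20 mg daily. The third gives 40 × 7 = 280 mg/week, below the level -4 floor of 400 mg/week. A prescriber who kept to the sentence would run out of permitted doses after two reductions, not four.

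**Other readings.** The rule does fit moves within one schedule (80 to 60 mg daily; 100 to 80 mg on 5 of 7 days), but each of those crosses two levels, and Table 11 orders one level at a time.

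**The case against.** The best reply is that the protocol already resolves this. The pointer to Table 5 follows at once, the table sits just below, and the Table 3 footnote, the four-level cap, Table 11 and Table 12 all speak in levels. No toxicity rule mentions 20 mg, so a prescriber told to drop one level will look it up and find the right dose. This stands as a limit on the practical risk. It does not make the sentence correct.

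One can also read the sentence as describing only the first reduction, since it is in the singular and follows the statement that everyone starts at level 0. On that reading it is true. But it refers to the current dose and not to the starting dose, so the wording does not support that limit.

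A fair criticism concerns the comparison from level -2: someone following the sentence from the start would never be at that level, and the sentence does not say that the 5-of-7 schedule is kept. The 4.8% is therefore a check of one step under a stated assumption, not a likely course of treatment. The comparison that carries weight is the one at the second reduction.

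Finally, the wrong dose is itself a listed level and is lower than intended, so no overdose results.

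**Conclusion.** The inconsistency is real and minor. The 20 mg sentence matches one of the four steps in Table 5, and at the second reduction it gives 16% less drug per week than the table (420 against 500 mg). Table 5 is not at fault: the protocol's other dose-reduction instructions lead to it or use its levels, and its title and the four-level cap already class levels -2 and -4 as reductions.

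The conclusion rests on reading the sentence as applying to any reduction, as its wording indicates, and on the doses as printed in Table 5. The documents do not say how often a second reduction is expected, so no number of affected patients can be given. PFS at 24 weeks as the primary endpoint, the 21 patients and the 12-of-21 criterion do not change.

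**What to change.** In Section 9.1, delete the 20 mg sentence or limit it to the first reduction, and state: *Dose reductions follow Table 5, one level at a time.* As an option, add that moving from level -1 to -2, or from -3 to -4, is not re-escalation even though the dose on a dosing day rises by 20 mg.

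The cost is one sentence in the next amendment. Table 5, Table 11, the sample size and the analysis stay as they are.

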6.1 Subject Inclusion Criteria

Patients eligible for inclusion in this study have to meet all the following criteria:

- Participants must be able to understand and be willing to sign a written informed consent document.
- Subjects must be at least 18 years of age on the day of consenting to the study.
- Histologically documented PCNSL or SCNSL. Patients with SCNSL need to have cytology or tissue biopsy documenting lymphomatous involvement of the CNS
- Patients must have relapsed/refractory PCNSL or relapsed/refractory SCNSL
- All patients need to have received at least one prior CNS directed therapy. There is no restriction on the number of recurrences.
- Patients with parenchymal lesions must have unequivocal evidence of disease progression on imaging (MRI of the brain or head CT) 21 days prior to study registration. For patients with leptomeningeal disease only, CSF cytology must document lymphoma cells and/or imaging findings consistent with CSF disease 21 days prior to study registration.
- Participants must have a Karnofsky performance status (KPS) of ≥ 50 .
- Participants must have adequate bone marrow and organ function shown by:

MEMORIAL SLOAN-KETTERING CANCER CENTER IRB PROTOCOL

IRB#: 14-177 A(5)

- Absolute neutrophil count (ANC) $\geq 1.5 \times 10^9/L$
- Platelets $\geq 100 \times 10^9/L$ and no platelet transfusion within the past 14 days prior to study registration
- Hemoglobin (Hgb) ≥ 9 g/dL and no red blood cell (RBC) transfusion within the past 14 days prior to study registration
- International Normalized Ratio (INR) ≤ 1.5
- Alanine aminotransferase (ALT) and aspartate aminotransferase (AST) ≤ 1.5 times the ULN.
- Serum bilirubin \leq upper limit of normal; or total bilirubin $\leq 2.0 \times$ the ULN with direct bilirubin within the normal range in patients with well documented Gilbert Syndrome.
- Participants must be able to take oral medication.
- Patients must be able to tolerate MRI scans.
- Patients must be able to tolerate lumbar puncture and/or Ommaya taps.
- Participants must have recovered to grade 1 toxicity from prior therapy.
- Participants must be able to submit 20 unstained slides from the initial tissue diagnosis for confirmation of diagnosis and correlative studies
- Life expectancy of > 3 months (in the opinion of the investigator)

Note: Prior autologous stem cell transplant as well as radiation to the CNS is **NOT** an exclusion criterion. Prior allogenic stem cell transplant **IS** an exclusion criterion.

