
*(LFTs include albumin, ALT, AST, total bilirubin (fractionated if total bilirubin > 2.0 x ULN), alkaline phosphatase (fractionated if alkaline phosphatase is grade 2 or higher) and GGT)
 
**In case of recurring Grade 3 or higher toxicity after re-challenge, patient should be permanently discontinued
 
***All patients with ALT or AST>3.0x ULN and total bilirubin >2.0x ULN in the absence of cholestasis must immediately be withdrawn from buparlisib and every attempt should be made to carry out the liver event follow-up assessments as described below in section 11.11.1.2: Management of Hepatotoxicity (ALT and/or AST> 3.0x ULN and total bilirubin >2.0x ULN) in patients receiving buparlisib and Viral Serology and other tests for hepatotoxicity follow-up.
 
Hepatic toxicity monitoring (*for patients with Gilbert Syndrome: total and direct bilirubin must be monitored, intensified monitoring applies to changes in direct bilirubin only; the monitoring includes the following LFTs: albumin, ALT, AST, total bilirubin (fractionated if total bilirubin > 2.0 x ULN), alkaline phosphatase (fractionated if alkaline phosphatase is grade 2 or higher) and GGT):
 
Cycle 1 and 2: every other week (if visit schedule allows a more frequent monitoring this should be considered) or more frequently if clinically indicated especially for patients with borderline acceptable AST/ALT, or bilirubin* values
 
Cycle 3 and onward: monthly or more frequently if clinically indicated
 
In case of any occurrence of ALT/AST, or bilirubin* increase ≥ grade 2 the liver function tests must be monitored weekly or more frequently if clinically indicated until resolved to ≤ grade 1
 
In case of any occurrence of ALT/AST, or bilirubin* increase ≥ grade 3 the liver function tests must be monitored weekly or more frequently if clinically indicated until resolved to ≤ grade 1; hereafter the monitoring should be continued every other week or more frequently if clinically indicated until the end of treatment with study medication
 
Patients who discontinued study treatment should be monitored weekly, including LFTs* or more frequently if clinically indicated until resolved to ≤ grade 1 or stabilization (no CTCAE grade change over 4 weeks).
	
ENDOCRINE/METABOLIC	
Fasting Plasma Glucose (FPG)	

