11.11 Liver Toxicity

11.11.1 Liver Toxicity Findings

A recent liver safety review across Novartis-sponsored trials with BKM120 identified several potentially drug-induced liver toxicity (DILI) cases (e.g. AST/ALT >3.0 x ULN and TBL >2.0 x ULN at any time during the treatment, regardless of causality). Upon medical review, most of these cases occurred in the context of disease progression in terminally ill, advanced cancer patients and/or were confounded by other causes. However, six of these DILI candidates were consistent with Hy's law criteria (e.g. AST/ALT >3.0x ULN and TBL >2.0xULN in the absence of cholestasis and other explanatory causes) with probable causal relationship to study treatment. Five of these cases were enrolled in study CBKM120F2302 in combination with fulvestrant, and one in combination with the investigational drug LDE225 (sonidegib). All patients have recovered upon treatment discontinuation except one patient for whom no data is available since the patient refused to return for safety follow-up.

Approximately 25 to 45% of patients treated with single agent BKM120 reported liver toxicity (all grades, regardless of study drug relationship, 100 mg/d dose) based on a search of multiple MedDRA event terms (e.g. SMQ preferred terms). The incidence of grade 3 and 4 events was approximately 10 to 30%. Liver function test (LFT) alterations observed during ongoing and completed studies have been mostly transaminase enzyme increases (ALT and/or AST). Data suggest a slightly higher rate of grade 3 and 4 liver enzyme elevations in Japanese patients (44%) in the [CBKM120X1101] study, however, the number of patients treated at 100 mg in this study was limited (n=9). Transaminase elevations typically occur during the first 6 to 8 weeks of treatment start.

Although transaminase increases are relatively common, only a few of the patients had other simultaneous observations related to impaired liver function (e.g. bilirubin increase or clinical symptoms).

Based on these findings, conservative inclusion criteria and guidelines to monitor and follow patients with LFT alterations (including dose and schedule modifications) have been implemented. Please refer to the respective inclusion/exclusion criteria and Table 11.0 in this protocol for more detailed guidelines.

11.11.1.2 Management of Hepatotoxicity (ALT and/or AST \geq 3.0x ULN and total bilirubin \geq 2.0x ULN) in patients receiving Buparlisib

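### For a participant with a Grade 1 AST/ALT baseline, Section 9.1 read plainly allows restart after a Grade 3 hold at up to 5.0 x ULN, where Table 11 allows only 3.0 x ULN

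*Combined protocol and SAP*

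**What the plan says.** Section 9.1 (Dose Modifications/Delays) covers laboratory toxicities that have led to a hold. If the participant already had an abnormal value at baseline, the toxicity can be considered "resolved from a hold perspective when it has resolved to within 1 grade of the baseline value". Baseline here means the last test before the first dose. An Exception follows: where the value within one grade of baseline "would still require a hold, continue to hold until resolution of toxicity to grade 1 or return to baseline". No laboratory test is excluded from the rule.

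Table 11 in Section 11.2 sets the AST/ALT rules, for bilirubin not above 2.0 x ULN:

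- Grade 2 (above 3.0 to 5.0 x ULN): "Can continue treatment at ↓ 1 dose level". This is not a hold.
- Grade 3 (above 5.0 to 20.0 x ULN): omit until Grade 1 or lower, then restart one dose level down. "If no recovery in ≤28 days, discontinue buparlisib permanently".
- Footnote: "In case of recurring Grade 3 or higher toxicity after re-challenge, patient should be permanently discontinued".
- Grade 4: permanent discontinuation.

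Section 6.1 requires "Alanine aminotransferase (ALT) and aspartate aminotransferase (AST) ≤ 1.5 times the ULN". A participant may therefore enter with a value above ULN, which Table 11 grades as Grade 1.

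**The concern.** The two sections give different restart limits for the same patient: one who starts with a mildly raised AST or ALT, reaches Grade 3, and falls back to between 3.0 and 5.0 x ULN. Under 9.1 the hold is over. Under Table 11 the drug stays off, and is stopped for good if the value has not come down to 3.0 x ULN or below in 28 days. Two investigators could each follow the protocol and act in opposite ways.

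The liver is where this drug calls for care. Section 11.11.1 says of liver toxicity on single-agent treatment: "The incidence of grade 3 and 4 events was approximately 10 to 30" percent. It also reports potential drug-induced liver injury across the manufacturer's trials, of which "six of these DILI candidates were consistent with" Hy's law with a probable causal link to study treatment. It then says that conservative eligibility and liver-test rules were put in place. The wording of 9.1 can loosen one of them. A patient restarted above 3.0 x ULN already meets the transaminase half of Table 11's combined permanent-stop criterion (AST/ALT above 3.0 with bilirubin above 2.0 x ULN).

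**Working it through.** The plan states no figure for this point. The check traces the rules and then bounds the number of patients.

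**Step 1. Restart ceiling after a Grade 3 AST/ALT hold, bilirubin at or below 2.0 x ULN**

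| Baseline AST/ALT | Table 11, Grade 3 row | Section 9.1, plain reading |
|---|---|---|
| Normal | 3.0 x ULN | Rule not triggered, so 3.0 x ULN |
| Grade 1 (above 1.0 to 1.5 x ULN at eligibility) | 3.0 x ULN | Grade 1 + 1 = Grade 2; Grade 2 is not a hold row, so the Exception is not triggered: 5.0 x ULN |

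**Step 2. Other laboratory rows, Grade 1 baseline**

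- Bilirubin and creatinine: Grade 2 is a hold row, so the Exception applies and the ceiling stays at Grade 1 (1.5 and 2.0 x ULN). There is no divergence.
- Neutrophils and platelets: Grade 2 is not a hold row, while Grade 3 and 4 are held to Grade 1 or lower. The same textual divergence exists.
- Fasting glucose, asymptomatic: 160 mg/dL under Table 11 against 250 mg/dL under 9.1. Table 11 also discontinues a patient who stays above Grade 1 for more than 7 days.

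**Step 3. Distance from restart to a recurrent Grade 3 (above 5.0 x ULN)**

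- From 3.0: 5.0/3.0 - 1 = 67%
- From 4.0: 5.0/4.0 - 1 = 25%

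These are distances to a threshold, not risks.

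**Step 4. How many of 21 patients**

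- Table 10, drug-related Grade 3/4 transaminase increase: 9/81 = 11.1%, exact 95% CI 5.2% to 20.0%. Times 21: 2.3 patients (1.1 to 4.2).
- Section 11.11.1, 10% to 30%: 21 x 0.10 = 2.1 and 21 x 0.30 = 6.3 patients. This range covers many liver event terms regardless of cause, so it is wider than the AST/ALT row.

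Both sources include Grade 4, which is stopped under either text. Only patients with an abnormal baseline count, and the documents do not give that share. Assuming a share s, and a risk that does not depend on baseline:

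| s | 2.33 x s (Table 10) | 6.3 x s (top of the 11.11.1 range) |
|---|---|---|
| 10% | 0.23 | 0.63 |
| 20% | 0.47 | 1.26 |
| 40% | 0.93 | 2.52 |

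One expected Grade 3/4 event in such a patient needs s = 1/2.33 = 43% at the Table 10 rate, 1/2.1 = 48% at 10%, or 1/6.3 = 16% at 30%. The count then falls further: the event must be Grade 3 and not 4, bilirubin must stay at or below 2.0 x ULN, and restart must come while the value is still at Grade 2.

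**The case against.** The best reply is that the protocol already shows which limit it means. Section 9.1 opens by sending toxicity interruptions to Table 11, and says that modifications rest on the worse preceding toxicity. On that footing the Grade 3 row still governs when the value has fallen to Grade 2, so Grade 2 would still require a hold and the Exception gives 3.0 x ULN. Section 11.11.1.2 refers to Section 11.2 for AST/ALT re-initiation and mentions no baseline exit. The 9.1 rule is also permissive, and is framed for holds to Grade 1 or baseline, whereas the AST/ALT row has no baseline limb.

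Most of this stands as evidence of intent. A reader might infer that the protocol leaves 3.0 and 5.0 x ULN equally supported; it does not, because these passages point to 3.0. They do not close the gap, however. If the Exception is always tested against the row that caused the hold, the 9.1 rule has almost no effect on any laboratory row. If the rule needs a baseline limb in the row, it reaches no laboratory row at all, since only the mood rows have one. A site may reasonably assume that the rule was written to do something.

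The stakes are also smaller than they first look. Table 11 accepts reduced dosing at above 3.0 to 5.0 x ULN for every Grade 2 patient. Even on the loose reading the restart is one level down, liver tests stay at least weekly until Grade 1, and the bilirubin and recurrent-Grade-3 stops remain. That stands, and it lowers the severity.

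**Conclusion.** The divergence is real but narrow. It concerns participants with a Grade 1 AST/ALT baseline, held for Grade 3 with bilirubin at or below 2.0 x ULN. For them the ceiling is 5.0 x ULN on the plain reading of 9.1 and 3.0 x ULN in Table 11. The rest of the protocol favours 3.0; 9.1 lacks the limit that would say so. Few patients are likely to be affected, though the number depends on a baseline share that the documents do not give. This is a low-severity safety correction.

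Four stronger conclusions might be inferred and are not supported:

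- *That 2.3 to 6.3 patients are exposed.* Those are all expected Grade 3/4 events, before the baseline and recovery filters.
- *That the Hy's law cases show the size of the risk here.* All six arose in combination treatment; this trial is single agent.
- *That bilirubin and glucose share the defect equally.* The Exception settles bilirubin. For glucose, 9.1 defines when a hold ends and does not claim to change the 7-day discontinuation trigger. The HbA1c exclusion (above 8%) and the advice in 11.4 to optimise control before starting also make badly raised baselines uncommon. It is a minor note.
- *That the efficacy result is at risk.* The PFS24w analysis and the 12-of-21 rule do not use the restart limit.

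**What to change.** Add one sentence to Section 9.1 after the Exception: *This baseline-relative rule does not apply to AST or ALT; after a Grade 3 AST/ALT hold, buparlisib is restarted only at ≤ Grade 1 and within 28 days, as stated in Table 11.*

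Bilirubin need not be named. The sentence should not say that the rule remains in force for neutrophils and platelets, because the same divergence exists there and such wording would endorse the looser restart by implication.

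One point for the sponsor to confirm: 9.1 elsewhere lets a participant who has benefited stay on after a 4-week delay if the Principal Investigator agrees. The new sentence would close that route for AST/ALT, in line with Table 11.

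The cost is one sentence and no extra tests, since AST and ALT are already measured at screening, on Cycle 1 Day 1 and weekly while raised to Grade 2 or higher. The downside is that a patient whose AST/ALT has recovered only to between 3.0 and 5.0 x ULN by day 28 loses the drug, as Table 11 already says. A sponsor who prefers 5.0 x ULN for raised baselines should write that into the Grade 3 row itself.
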